9.4 List of expected adverse events related to Eltrombopag

1. Thrombotic episodes related to thrombocytosis.
2. Allergic reactions (rash; hives; itching; difficulty breathing; tightness in the chest; swelling of the mouth, face, lips, or tongue);
3. Abnormal liver function tests (possible liver damage-ascitis, jaundice).
4. New onset of bone marrow fibrosis.
5. Stroke symptoms (e.g., confusion, slurred speech, sudden vision changes, one-sided weakness).
6. Muscle aches or pain (arms and/or legs).
7. Bleeding problems after discontinuation of treatment.

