Toxicity

In clinical studies, eltrombopag was well tolerated with modest toxicity, which are detailed in the enclosed "Investigator's Brochure" and summarized here. More than 1000 patients have been treated on various clinical efficacy studies with doses of eltrombopag ranging from 3 mg to 300 mg given for 1- 560 days. In placebo controlled ITP studies, only nausea and vomiting occurred more frequently (>5%) in eltrombopag treated subjects than placebo. These were mild and resolved without treatment. No significant difference between the two groups was seen in the incidence of other adverse events or serious adverse events. Mild, reversible, abnormalities of liver function tests (AST, ALT, ALP, and Bilirubin) were noted (10% eltrombopag vs 7% placebo) in ITP studies but were infrequently seen in HCV studies and chemotherapy related thrombocytopenia studies. Increase in reticulin and collagen in bone marrow biopsy was seen in some subjects but was not clinically relevant.^[46,47] Likewise no difference in cataract incidence was reported between patient and controls.^[48] No increase in incidence of malignancies was seen in patients receiving the drug. Transient decrease in platelet count following discontinuation of the drug was seen, but this was not associated with clinically meaningful bleeding events. In summary, eltrombopag is well tolerated without any major dose dependent adverse effects.

Rationale for dose

1. The effective dose in subjects with thrombocytopenia post stem cell transplantation is unknown, and 300 mg is the maximum dose that is currently being considered in eltrombopag studies for patients with chemotherapy-induced thrombocytopenia, myelodysplastic syndrome (MDS), acute myelogenous leukemia (AML) and advanced sarcoma. Four studies recently reported safety of this dose including one in patients undergoing stem cell transplantation.^[49-52]

2. In healthy subjects, a clear dose and exposure response was seen for eltrombopag doses of 10 mg to 200 mg once daily for 5 days, with geometric mean AUC values of 302 $\mu\text{g.h/mL}$ for the 200 mg once daily regimen. Eltrombopag was well tolerated in healthy subjects at all dose levels.
3. In ITP subjects, a dose response was seen for eltrombopag doses of 30 mg to 75 mg once daily, with geometric mean AUC values of 169 $\mu\text{g.h/mL}$ for the 75 mg once daily regimen. There was no significant difference between the safety profile of ITP subjects receiving 30, 50 or 75 mg of eltrombopag.

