9.3 Collection of adverse events

Only those events known to be caused by Eltrombopag will be recorded in the designated case report form (PDMS/CORE). Collection of adverse events will reflect the onset and resolution date and maximum grade. Intermittent events should be labeled as such and followed until resolution. If a patient is taken off study while an event still ongoing, this will be followed until resolution unless another therapy is initiated.

Events known to be caused by components of the transplant package and its direct consequences as well as those events known to be related to drugs used for the treatment of GVHD, infections and supportive treatment will not be collected in the designated case report form/database. Concurrent medications considered standard of care for transplant patients will not be captured in the case report form. They will be documented in the medical record.

Adverse events related to the study drug will be collected and recorded for the duration of active treatment plus 30 days.

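### Section 9.4 omits nausea and vomiting, which Section 3.0 reports as more frequent on eltrombopag than placebo, so non-serious cases may go unrecorded under Section 9.3

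*Combined protocol and SAP*

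**What the plan says.** Section 3.0, under Toxicity, summarises earlier experience: "In placebo controlled ITP studies, only nausea and vomiting occurred more frequently (>5%) in eltrombopag treated subjects than placebo". It adds: "These were mild and resolved without treatment". For the rest it says "No significant difference between the two groups was seen in the incidence of other adverse events or serious adverse events", and then gives one pair of rates: "Mild, reversible, abnormalities of liver function tests (AST, ALT, ALP, and Bilirubin) were noted (10% eltrombopag vs 7% placebo) in ITP studies".

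Section 9.4, "List of expected adverse events related to Eltrombopag", has seven items: thrombotic episodes, allergic reactions, liver test abnormalities, new marrow fibrosis, stroke symptoms, muscle pain, and bleeding after the drug is stopped. Nausea and vomiting are not among them.

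Section 9.2 scores events known to be caused by eltrombopag as definitely related. It scores events known to be caused by the transplant package, or by drugs for GVHD, infection or supportive care, as unrelated. Where a relationship cannot be excluded, the event may be called possibly related. The PI decides.

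Section 9.3 opens its collection rule with "Only those events known to be caused by Eltrombopag will be recorded in the designated case report form" and excludes the transplant and supportive-care events. Its last paragraph describes the events to be collected as those related to the study drug.

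**The concern.** The list of expected drug effects disagrees with the protocol's own account of the drug. The two events for which Section 3.0 states an excess over placebo are missing, while events with weaker stated support are present.

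Safety is the first secondary objective, and Section 8.0 plans descriptive toxicity summaries. These can show only what was entered in the database. If staff use 9.4 as the working guide to known drug effects, non-serious nausea or vomiting during the transplant period may be put down to transplant and never entered.

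Vomiting also bears on dose delivery. Under Section 8.0, patients who miss the drug for more than 10 days are left out of the primary analysis and replaced, so tolerability data would help to explain who was excluded.

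**Working it through.** The point rests on no sample size, power or error rate. The check is a comparison of sections, plus one subtraction.

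**Step 1. Section 3.0 (Toxicity) against Section 9.4.**
- Nausea and vomiting: more frequent than on placebo in ITP studies; not listed.
- Liver tests: 10% against 7%; listed ("Abnormal liver function tests (possible liver damage-ascitis, jaundice").
- Marrow reticulin and collagen: increases in some subjects, judged not clinically relevant; marrow fibrosis is listed.
- Fall in platelets after stopping: not linked to meaningful bleeding; bleeding after stopping is listed.
- Thrombosis, allergy, stroke symptoms, muscle pain: not mentioned in that summary; listed, perhaps from the Investigator's Brochure, which is not available here.

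Mild events such as muscle aches are on the list, so mildness does not explain the omission. Neither does weak evidence, since fibrosis and bleeding after stopping are on it.

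**Step 2. How far the word only in Section 3.0 can be pressed.** The liver test excess is 10% − 7% = 3 percentage points. If the 5% qualifier means a between-group difference, 3 is below 5 and the sentence is consistent with the liver figures. If it means an incidence above 5%, liver tests at 10% also qualify and the word is not literally true. The text does not say which is meant. On either reading nausea and vomiting were more frequent on eltrombopag.

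**Step 3. Trace a non-serious case of nausea through 9.2 and 9.3.** Assume, as general clinical knowledge that the documents do not state, that conditioning and supportive drugs can also cause it.
- Treated as a known drug effect: definitely related, recorded.
- Treated as a known transplant or supportive-drug effect: unrelated, not recorded.
- Cause cannot be excluded: may be called possibly related. The opening rule of 9.3 (known to be caused) would leave it out; its last paragraph (related) could bring it in.

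No rule says which route applies when both causes are known ones. The result depends on the assessor.

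**Step 4. Whether other records fill the gap.**
- Serious cases: yes. Section 9.6 requires all SAEs to go to the IND Office regardless of attribution.
- Dose delivery: in part. Section 5.0 has outpatients log vomited doses in a diary, and requires days missed and the reason to be documented when a patient cannot take oral drug.
- Grade and attribution: entered in the medical record under 9.2, not necessarily in the database.
- Antiemetic use as a proxy: no. Concomitant medications are not entered in the database.

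**Step 5. The stopping rule.** Section 8.0 counts only drug-attributable non-hematologic toxicity of grade 4 or higher. Events that Section 3.0 calls mild would rarely reach it.

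**The case against.** The strongest reply is that 9.4 controls nothing. No section declares it exhaustive or says that it decides attribution or collection. Section 9.3 turns on whether an event is known to be caused by eltrombopag, and Section 3.0 itself supplies that knowledge for nausea and vomiting. Section 9.2 offers both definitely and possibly related, with the PI as final arbiter. This stands, and it limits the claim to what may happen.

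A reader might infer more on four counts, none of which the documents support.
- That these events will default to transplant and vanish from the safety data. The text leaves attribution open, and serious cases are reported in any event.
- That leaving them off 9.4 makes them unexpected for expedited reporting under 9.6. The 24-hour report to the IND Office and the reports to the manufacturer require an event to be both unexpected and related, so an event scored as unrelated triggers neither. The documents also do not say whether 9.4 or the Investigator's Brochure defines expectedness.
- That the trial dose, 300/75 = 4 times the highest ITP dose cited, makes the omission more serious. Section 3.0 concludes that there are no major dose-dependent adverse effects and cites four studies reporting the safety of 300 mg.
- That every case should be collected whatever its attribution. Neither arm has a concurrent untreated control, so full collection could not separate drug-caused cases from background. It is a debatable extra.

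The reply does not remove the disagreement between 3.0 and 9.4, or the two wordings in 9.3.

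**Conclusion.** The point holds in limited form. Section 9.4 is inconsistent with Section 3.0, and 9.3 does not settle what happens to an event with two possible causes. Non-serious nausea and vomiting may therefore be under-recorded and missing from the toxicity summaries by arm. The primary analysis rules and SAE reporting are unchanged, and the grade 4 stopping rule is unlikely to be affected.

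The size cannot be estimated from the documents. A reader might take the 5% qualifier as a five-point excess and apply it to the maximum haploidentical enrolment: 55 × 0.05 = 2.75, about 3 patients. That assumes a reading of the qualifier that the text does not confirm, a carry-over from ITP patients to transplant recipients, and, if all are counted as lost, that every case is scored unrelated. It should not be cited as an estimate.

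The conclusion rests on two assumptions: that transplant treatment or supportive drugs can also cause these symptoms, and that some assessors would follow the narrower wording in 9.3. The correction is worth making because it costs little and decides what the safety dataset contains.

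**What to change.** 1. Add nausea and vomiting to the list in Section 9.4, so that it agrees with Section 3.0.
2. In Section 9.3, replace the two wordings with one rule: adverse events judged definitely or possibly related to eltrombopag are recorded by maximum grade with onset and resolution dates. State that this includes nausea and vomiting even when transplant is another possible cause.
3. In Section 8.0, summarise these two events by arm beside missed and vomited doses.

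The cost is two terms in 9.4, a sentence each in 9.3 and 8.0, and a little more data entry. The reported adverse event rate will include some cases caused by transplant, and the summary should say so. No dose or treatment rule changes.

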9.5 Treatment Duration Definitions

Active Treatment: the therapy administered to the participant as specified in the "Dosage and Administration" part of the proposal. Supportive care and standard forms of post-transplant immunosuppressive therapy are not considered active treatment.

Last day of "Active Treatment": is the last day of the study intervention.

Active Treatment Period: is the period of time from the first day of "Active Treatment" until 30 days after the "Last day of Active Treatment" as specified above.

Follow-up Period is the period of time that immediately follows the end of the "Active Treatment Period." This period ends when the patient is removed from the study.

9.6 Reporting Requirement

Serious Adverse Event Reporting (SAE) Language

An adverse event or suspected adverse reaction is considered "serious" if, in the view of either the investigator or the sponsor, it results in any of the following outcomes:

- Death
- A life-threatening adverse drug experience – any adverse experience that places the patient, in the view of the initial reporter, at immediate risk of death from the adverse experience as it occurred. It does not include an adverse experience that, had it occurred in a more severe form, might have caused death.
- Inpatient hospitalization or prolongation of existing hospitalization
- A persistent or significant incapacity or substantial disruption of the ability to conduct normal life functions.
- A congenital anomaly/birth defect.

Important medical events that may not result in death, be life-threatening, or require hospitalization may be considered a serious adverse drug experience when, based upon appropriate medical judgment, they may jeopardize the patient or subject and may require medical or surgical intervention to prevent one of the outcomes listed in this definition. Examples of such medical events include allergic bronchospasm requiring intensive treatment in an emergency room or at home, blood dyscrasias or convulsions that do not result in inpatient hospitalization, or the development of drug dependency or drug abuse (21 CFR 312.32).

Important medical events as defined above, may also be considered serious adverse events. Any important medical event can and should be reported as an SAE if deemed appropriate by the Principal Investigator or the IND Sponsor, IND Office.

· All events occurring during the conduct of a protocol and meeting the definition of a SAE must be reported to the IRB in accordance with the timeframes and procedures outlined in "The University of Texas M. D. Anderson Cancer Center Institutional Review Board Policy for Investigators on Reporting Unanticipated Adverse Events for Drugs and Devices". Unless stated otherwise in the protocol, all SAEs, expected or unexpected, must be reported to the IND Office, regardless of attribution (within 5 working days of knowledge of the event).

· **All life-threatening or fatal events**, that are unexpected, and related to the study drug, must have a written report submitted within **24 hours** (next working day) of knowledge of the event to the Safety Project Manager in the IND Office.

· **Unless otherwise noted, the electronic SAE application (eSAE) will be utilized for safety reporting to the IND Office and MDACC IRB.**

· **Serious adverse events will be captured from the time of the first protocol-specific intervention, until 30 days after the last dose of drug, unless the**

participant withdraws consent. Serious adverse events must be followed until clinical recovery is complete and laboratory tests have returned to baseline, progression of the event has stabilized, or there has been acceptable resolution of the event.

- Additionally, any serious adverse events that occur after the 30 day time period that are related to the study treatment must be reported to the IND Office. This may include the development of a secondary malignancy.**

Reporting to FDA:

- Serious adverse events will be forwarded to FDA by the IND Sponsor (Safety Project Manager IND Office) according to 21 CFR 312.32.**

It is the responsibility of the PI and the research team to ensure serious adverse events are reported according to the Code of Federal Regulations, Good Clinical Practices, the protocol guidelines, the sponsor's guidelines, and Institutional Review Board policy.

Reporting to Novartis Pharmaceuticals Corporation:

The institution and investigator shall report to Novartis Pharmaceuticals Corporation within **24 hours** (next working day) of knowledge of the unexpected and related event: all life threatening or fatal events; and within five (5) working days of knowledge of the unexpected and related event any adverse drug experience, as defined by applicable law or regulation, or pregnancy experienced by any study subject receiving a Novartis Pharmaceuticals Corporation study drug(s).

